8.2 Secondary Objectives

There are multiple secondary objectives, where secondary objectives 1-4 examine treatment effectiveness and secondary objectives 5-8 treatment safety. Hence, the secondary objectives compare rhFSH-alfa reference product with HP-hMG or rhFSH-alfa biosimilar products regarding the following outcomes:

1. a) CPR and OPR per initiated IVF/ICSI stimulation cycle, and b) cumulative clinical pregnancy rate (CCPR) and COPR per initiated IVF/ICSI stimulation cycle

2. Number of oocytes retrieved, embryos transferred, embryos cryopreserved, and utilizable embryos per initiated IVF/ICSI stimulation cycle and per oocyte retrieval cycle
3. Implantation rate

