Set 4	Stimulation cycles with drug of interest aspirated on or before 30 November 2020 ⁺	Secondary objective 2	Oocytes retrieved per aspirated stimulation cycle
			Embryos cryopreserved per aspirated stimulation cycle
			Utilizable embryos per aspirated stimulation cycle
Set 5	Stimulation cycles with drug of interest initiated on or before 31 August 2020 ⁺	Secondary objective 8	OHSS
Set 6	Fresh and frozen embryo transfers linked to stimulation cycles with drug of interest occurring on or before 31 December 2020 ⁺	Secondary objective 2	Fresh embryos transferred
			Frozen embryos transferred
Set 7	Fresh and frozen embryo transfers linked to stimulation cycles with drug of interest occurring on or before 30 September 2020 ⁺	Secondary objective 3	Implantation rate
Set 8	Women who initiated their first-ever stimulation cycle with drug of interest on or before 31 December 2019	Primary objective	MC-CLBR
		Secondary objective 4	TTLB

CCPR: cumulative clinical pregnancy rate; CLBR: cumulative live birth rate; CPR: clinical pregnancy rate; COPR: cumulative ongoing pregnancy rate; FET: frozen embryo transfer; LBR: live birth rate; MC-CLBR: multiple-cycle cumulative live birth rate; OPR: ongoing pregnancy rate; OHSS: ovarian hyperstimulation syndrome; TTLB: time-to-live birth.

Notes:

*Should data on initiated cycles from the Swedish Q-IVF be available only through 31 December 2019, this analysis set will be adjusted to the same day and month in 2019.

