		Per aspirated stimulation cycle	Set 4	Number (see section 9.7.3.3)

Study objective	Outcome	Unit of analysis	Analysis set	Analysis results
				Adjusted OR (see section 9.7.3.4) Stratified analysis (see section 9.7.3.6)
	Number of embryos transferred	Per fresh embryo transfer	Set 6	Number (see section 9.7.3.3) Adjusted OR (see section 9.7.3.4)
		Per frozen embryo transfer	Set 6	Number (see section 9.7.3.3) Adjusted OR (see section 9.7.3.4)
	Number of embryos cryopreserved	Per initiated stimulation cycle	Set 3	Number (see section 9.7.3.3) Adjusted OR (see section 9.7.3.4)
		Per aspirated stimulation cycle	Set 4	Number (see section 9.7.3.3) Adjusted OR (see section 9.7.3.4)
	Number of utilizable embryos	Per initiated stimulation cycle	Set 3	Number (see section 9.7.3.3) Adjusted OR (see section 9.7.3.4)
		Per aspirated stimulation cycle	Set 4	Number (see section 9.7.3.3) Adjusted OR (see section 9.7.3.4)
Secondary objective 3	Implantation rate	Per embryos transferred per stimulation cycle	Set 7	Rate (see section 9.7.3.3) Adjusted OR (see section 9.7.3.4)
Secondary objective 4	Time-to-live birth	Per woman per up to five stimulation cycles with the same drug	Set 8	Kaplan-Meier plots and estimates (see section 9.7.3.5) Adjusted live birth rate ratios (see section 9.7.3.5)
Secondary objective 5	Rate of pregnancy loss	Per clinical pregnancy following embryo transfer	Set 2	Rate (see section 9.7.3.3) Adjusted OR (see section 9.7.3.4)
Secondary objective 6	Multiple pregnancy rate	Per clinical pregnancy following embryo transfer	Set 2	Rate (see section 9.7.3.3) Adjusted OR (see section 9.7.3.4)

Study objective	Outcome	Unit of analysis	Analysis set	Analysis results
Secondary objective 7	Cycle cancellation rate	Per initiated stimulation cycle	Set 3	Rate (see section 9.7.3.3) Adjusted OR (see section 9.7.3.4)
Secondary objective 8	OHSS rate	Per initiated stimulation cycle	Set 5	Rate (see section 9.7.3.3) Adjusted OR (see section 9.7.3.4)
Secondary objective 9	Treatment-associated costs	Per initiated stimulation cycle	Set 2	Descriptive cost analysis (see section 9.7.3.7)

CCPR: cumulative clinical pregnancy rate; CLBR: cumulative live birth rate; CPR: clinical pregnancy rate; COPR: cumulative ongoing pregnancy rate; LBR: live birth rate; MC-CLBR: multiple-cycle cumulative live birth rate; OPR: ongoing pregnancy rate; OHSS: ovarian hyperstimulation syndrome; OR: odds ratio.

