Secondary objective 1	CPR	Number of clinical pregnancies after fresh embryo transfer	Initiated cycles with drug of interest
	CCPR	Number of clinical pregnancies after one initiated stimulation cycle, including all fresh or frozen embryo transfers linked to that cycle	Initiated cycles with drug of interest
	OPR	Number of ongoing pregnancies after fresh embryo transfer	Initiated cycles with drug of interest
	COPR	Number of ongoing pregnancies after one initiated stimulation cycle, including all fresh or frozen embryo transfers linked to that cycle	Initiated cycles with drug of interest
Secondary objective 2	Number of oocytes retrieved	Number of oocytes retrieved	Initiated cycles with drug of interest
		Number of oocytes retrieved	Aspirated cycles with drug of interest

Study objective	Outcome measure	Numerator	Denominator
	Number of embryos transferred	Number of fresh embryos transferred	Fresh embryo transfers linked to cycles with drug of interest
		Number of frozen embryos transferred	Frozen embryo transfers linked to cycles with drug of interest
	Number of embryos cryopreserved	Number of embryos cryopreserved	Initiated cycles with drug of interest
		Number of embryos cryopreserved	Aspirated cycles with drug of interest
	Number of utilizable embryos	Number of utilizable embryos	Initiated cycles with drug of interest
		Number of utilizable embryos	Aspirated cycles with drug of interest
Secondary objective 3	Implantation rate	Number of intrauterine gestational sacs after one fresh or frozen embryo transfer	Number of embryos transferred in one cycle
Secondary objective 4	TTLB	Time to first delivery with at least one live birth in up to five stimulation cycles with the same study drug, including all fresh or frozen embryo transfers linked to each of those stimulation cycles	N/A; conducted as time-to-event analysis; unit of analysis is women who initiated stimulation cycles with drug of interest
Secondary objective 5	Rate of pregnancy loss	Number of induced and spontaneous abortions	Clinical pregnancies with drug of interest following fresh or frozen embryo transfer
Secondary objective 6	Multiple pregnancy rate	Number of multiple pregnancies	Clinical pregnancies with drug of interest following fresh or

Study objective	Outcome measure	Numerator	Denominator
			frozen embryo transfer
Secondary objective 7	Cycle cancellation rate	Number of canceled cycles	Initiated cycles with drug of interest, including any linked initiated FET cycles

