will be analyzed both per initiated stimulation cycle and per aspirated stimulation cycle: number of oocytes retrieved and number of utilizable embryos (*i.e.*, a subset of secondary objective 2 outcomes). Number of embryos transferred (*i.e.*, a secondary objective 2 outcome) will also be considered as a count outcome in statistical models and will be analyzed per fresh and frozen embryo transfers. For modelling the count data appropriately, the distribution of count data will be checked by counting the mean and the variance of the data and the possibility of excess zeros in the count data will be evaluated visually by plotting the distribution of the data.

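### Secondary objective 2 asks for embryos transferred per cycle, but the analysis sections compare this count only per embryo transfer, so the stated comparison is not produced for that component

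*Protocol*

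**What the plan says.** The objective, in 8.2 and equally on the cover page and in the abstract, is: "Number of oocytes retrieved, embryos transferred, embryos cryopreserved, and utilizable embryos per initiated IVF/ICSI stimulation cycle and per oocyte retrieval cycle". The closing qualifier governs all four counts.

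The analysis of embryos transferred is fixed in four places, all with the transfer as unit:

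- **Table 5 (9.7.1), Set 6:** "Fresh and frozen embryo transfers linked to stimulation cycles with drug of interest occurring on or before 31 December 2020".
- **Table 6 (9.7.3):** "Per fresh embryo transfer" and "Per frozen embryo transfer", both on Set 6.
- **Table 7 (9.7.3.3):** the denominator for fresh embryos is "Fresh embryo transfers linked to cycles with drug of interest", with a matching entry for frozen embryos.
- **9.7.3.4:** the number of embryos transferred "will also be considered as a count outcome in statistical models and will be analyzed per fresh and frozen embryo transfers".

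The other components follow the objective. Tables 5 to 7 place oocytes retrieved, embryos cryopreserved and utilizable embryos on initiated cycles (Set 3) and aspirated cycles (Set 4). Section 9.7.3.4 says of two of them that they "will be analyzed both per initiated stimulation cycle and per aspirated stimulation cycle: number of oocytes retrieved and number of utilizable embryos".

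**The concern.** Section 9.2.2 makes initiation sufficient for a cycle to join a cohort; reaching a transfer is not required. Set 6 is a list of transfers. A cycle that was cancelled, gave no usable embryo, or had all its embryos frozen has no fresh-transfer row, so it is absent from the fresh count when the objective would have it contribute zero. A cycle followed by several frozen transfers appears several times.

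Reaching a transfer comes after the choice of drug and may depend on it. The protocol treats one route to no transfer, cycle cancellation, as an outcome to be compared between drugs (secondary objective 7). The per-transfer mean therefore answers a different question: how many embryos are placed, given that a transfer takes place. That number cannot be zero. It also reflects transfer policy, which 9.1.1 describes as moving from double towards elective single transfer over the study years. A drug difference in how many cycles get as far as a transfer cannot show in it.

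At stake is a mislabelled secondary result: a per-transfer ratio reported under an objective that promises a per-cycle one.

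**Working it through.** The protocol states no figure for this outcome, so there is nothing to reproduce. The check has two parts.

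**1. Unit required against unit planned**

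| Component of objective 2 | Unit in 8.2 | Unit in Tables 5 to 7 |
|---|---|---|
| Oocytes retrieved | initiated and retrieval cycle | initiated (Set 3), aspirated (Set 4) |
| Embryos cryopreserved | same | initiated (Set 3), aspirated (Set 4) |
| Utilizable embryos | same | initiated (Set 3), aspirated (Set 4) |
| Embryos transferred | same | fresh transfer, frozen transfer (Set 6) |

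Only the last row disagrees, and it does so in all three tables and in the text of 9.7.3.4. No section gives embryos transferred a per-cycle analysis.

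**2. What the change of unit does to a ratio**

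For fresh transfers, let *p* be the share of initiated cycles that reach a transfer and *m* the mean number of embryos per transfer. Then

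- mean per initiated cycle = *p* × *m*
- per-cycle ratio, drug A to drug B = (*p*A / *p*B) × (*m*A / *m*B)
- per-transfer ratio = *m*A / *m*B

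The two differ by the factor *p*A / *p*B. The same identity holds per aspirated cycle, with *p* taken among aspirated cycles.

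The protocol gives neither *p* nor *m*. **Assumptions for illustration:** *m* = 1.1 in both cohorts (the value cancels) and the shares below.

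| *p*A v *p*B | Mean per initiated cycle, A v B | Per-cycle ratio | Per-transfer ratio |
|---|---|---|---|
| equal | equal | 1.00 | 1.00 |
| 80% v 78% | 0.880 v 0.858 | 0.80/0.78 = 1.026 | 1.00 |
| 80% v 75% | 0.880 v 0.825 | 0.80/0.75 = 1.067 | 1.00 |
| 82% v 75% | 0.902 v 0.825 | 0.82/0.75 = 1.093 | 1.00 |

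The per-transfer column is 1.00 because *m* was set equal. The table shows what the planned unit cannot detect; it does not predict the data. If the shares are equal, the choice of unit makes no difference to the ratio.

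**The case against.** **The error may lie in the objective.** Four places use the transfer consistently, against one shared qualifier at the end of a four-item list. This is a fair point: the per-transfer comparison may be what was meant. The two parts of the protocol still disagree, and one of them must change. The SAP cannot be relied on to fill in a missing detail here, because the protocol itself fixes set, unit and denominator.

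**Utilizable embryos cover the gap.** They are defined in 9.1.2.2 as transferred plus cryopreserved embryos and are analysed per initiated and per aspirated cycle. This stands in part: cycles without a transfer do enter that analysis, and freeze-all cycles are credited. A sum does not, however, report its transferred component.

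**An advantage in reaching transfer would show elsewhere.** It could appear in cycle cancellation, in utilizable embryos, and in the live birth and pregnancy rates that Table 7 sets per initiated cycle. This also stands. A reader might infer that the plan hides such an advantage altogether; the documents support that only for this one count.

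**Weighting deals with the selection.** A reader might infer that covariate balance is lost among transfers. Section 9.7.3.1 has the propensity score weighting redone and checked in each analysis set, so measured covariates can be balanced within Set 6. That does not remove the conditioning on a post-treatment event or restore the per-cycle comparison.

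**Conclusion.** The inconsistency is real and is confined to one of the four components of secondary objective 2. As written, the stated per-cycle comparison of embryos transferred will not be produced, and cycles without a transfer drop out of the comparison that replaces it. The primary objective is unaffected.

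Its size cannot be derived from the protocol. Under the assumed transfer shares and equal embryos per transfer, per-cycle ratios of 1.03 to 1.09 would appear as 1.00.

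Two stronger readings are not supported. Objective 2 as a whole does not go unanswered, since Tables 5 to 7 give the other three components per cycle. Nor can these ratios be judged against the 5% difference called clinically meaningful in 9.5: that figure is given for the multiple-cycle cumulative live birth rate, and no threshold is set for embryo counts.

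**What to change.** In Tables 5, 6 and 7 and in 9.7.3.4:

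- Add the number of fresh embryos transferred per initiated cycle (Set 3) and per aspirated cycle (Set 4). Count cycles without a fresh transfer as zero and use the weights estimated for those sets.
- State that these results are read alongside utilizable embryos, because a freeze-all cycle counts as zero fresh embryos although it yielded usable ones.
- Keep the per-fresh-transfer and per-frozen-transfer analyses on Set 6 as supplementary comparisons. Section 9.1.2.2 applies this outcome to both kinds of transfer, so the frozen ones should not leave the comparison.

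If only the per-transfer comparison is intended, reword objective 2 for this component on the cover page, in the abstract and in 8.2, so that no per-cycle conclusion is drawn.

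The cost is a wording change and additional model runs on analysis sets that already exist. No new data are needed: computing utilizable embryos on Sets 3 and 4 already requires the transferred count for each cycle.

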9.7.3.5 Time-to-Live Birth Analysis

TTLB (secondary objective 4) will be analyzed restricting to women who initiated their first-ever stimulation cycle during the study period. As per study design, only the first five stimulation cycles (including all cycles of fresh or frozen embryo transfers) with the same study drug will be considered. The stimulation cycle rank number will be employed as the unit of time. Women will be followed until the first delivery with at least one live birth linked to treatment with the drug of interest, the sixth stimulation cycle, switch to another drug used for COS, diagnosis of breast, ovarian or uterine cancer, death, emigration (Denmark only) or end of study, whichever occurs first.

To estimate the TTLB in the original and IPTW-weighted study cohorts, survival analysis will be performed with the Kaplan-Meier method to estimate the time to the first live birth, expressed as the rank number of the stimulation cycle with the given study drug. The resulting Kaplan-Meier plots together with the estimated mean (with 95% CI) and median (with 95% CI) time-to-events will be presented.

For the comparison of the study cohorts, the time-to-live birth rate ratios adjusted for confounding factors, will be estimated by taking into account the IPTWs and using Cox proportional hazards regression model. The Cox model will be weighted with the IPTWs, and any variables included in the PS that are still unbalanced after weighting will be included as covariates for the Cox model. Additionally, the Cox model may be used to adjust the rate ratios for any other potential covariates that are assessed after the start of the stimulation cycle and hypothesized to be associated with the given study outcomes (see Table 1 in Section 9.3.2).

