The overall study period will be between 2010 and 2020. Different study period starts will be applied depending on which two drugs are being compared. For the comparison between rhFSH-alfa reference product and HP-hMG, the study period will start 1 January 2010 for both countries. This date is selected to ensure the study is sufficiently powered while also reducing heterogeneity in patient management over time. Changes that have occurred over time include moving towards vitrification rather than slow freezing for embryo cryopreservation and hence also moving from cleavage stage to blastocyst embryo transfers, elective single embryo transfers rather than double embryo transfers, and antagonist protocols rather than agonist protocols. For the comparison between rhFSH-alfa reference product and rhFSH-alfa biosimilar products, the study period will start 26 March 2014 for Denmark and 20 June 2014 for Sweden. These are the earliest dates when a rhFSH-alfa biosimilar product (Bemfola) received reimbursement status in each country. For

Sweden, where the IVF register is updated annually and has a lag time of approximately two years (see Section 9.4.2), inclusion of women undergoing IVF/ICSI treatment may end on 31 December 2019, depending on data availability at the time of data extraction. No such general restriction will be applied for Denmark, as the IVF register is updated monthly. In terms of follow-up of IVF/ICSI treatment and pregnancy outcomes, the study will end on 31 December 2020 (or last available date) for each country. Specifically, for the main analyses of the primary objective (LBR, CLBR and MC-CLBR) and secondary objective 4 (TTLB), a minimum follow-up period of 1 year has been chosen to allow sufficient time to achieve (at least) one live birth and a reasonable number of complete cycles for reliable estimates of live birth rates. Hence, the corresponding analyses are restricted to cycles initiated on or before 31 December 2019 (Sets 1 and 5 in Table 5). The minimum follow-up period will be extended to 2 years in a sensitivity analysis to explore the potential effect this has on the estimated MC-CLBR and TTLB (see sensitivity analysis 3 in Table 8).

To reduce possible bias linked to confounding by baseline characteristics, inverse probability of treatment weighting (IPTW), based on propensity scores (PS) (22), will be used to balance the distribution of potential confounders across the study cohorts.

Figure 1. Study design

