9.2.3 Study Time Periods

The overall **study period** is from 2010 through 2020. Different start dates are defined based on which two drugs are compared and, for the comparison with rhFSH-alfa biosimilar products, which country is analyzed. The study period ends on 31 December 2020 (or last available data) for both study drug comparisons and countries. Homogeneity in patient management over time, market entry of the comparator drugs and register lag times determine the start and end dates of the study period:

- rhFSH-alfa reference product vs. HP-hMG:
 - o Denmark, Sweden: 1 January 2010 – 31 December 2020
- rhFSH-alfa reference product vs. rhFSH-alfa biosimilar products:
 - o Denmark: 26 March 2014 – 31 December 2020
 - o Sweden: 20 June 2014 – 31 December 2020

For Sweden, inclusion of eligible women may need to be restricted to 31 December 2019, considering study timelines (see Section 6) and the typical two-year lag time for data availability from the Swedish National Quality Registry of Assisted Reproduction (Q-IVF) (see Section 9.4.2).

The overall **index date** is the date when the woman's *first* eligible IVF/ICSI stimulation cycle started (defined as start of ovarian stimulation) in the study period. The **stimulation cycle index date** is the date when each stimulation cycle started. For FET cycles linked to an included stimulation cycle, the cycle start date is the Last Menstrual Period (LMP) date for natural FET cycles or the date hormonal stimulation (replacement) treatment was started for stimulated FET cycles, as recorded in each country's IVF register.

The **baseline period** is defined as the 36-month minimum period prior to and including the (stimulation cycle) index date. During this period, (cycle) eligibility will be determined, and baseline covariates assessed. The baseline period may include time before the age of 18 years, for women who had IVF/ICSI treatment specifically at the age of 18 years. All available data from the registers will be used to obtain information on important covariates. Baseline data from the national patient registers, however, will be limited to the period in which ICD-10 coding has been

used comprehensively in each country (starting from 1994 in Denmark and 1998 in Sweden). The exact length of the baseline period will therefore vary between cycles within the same patient.

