the Danish National Board of Health suspected that were to some degree an under ascertainment of the true number of treatments initiated due to incomplete capture, noting that the use of electronic capture in future updates would improve quality (55,56). However, as only electronic reports are included during the period under study (2010-2020), previously identified limitations related to underreporting would not be an issue in this study. All treatment cycles and measurements on pregnancies from private and public IVF clinics are required to be reported, and the DIVF during the study period is based on electronic capture and complete and validated data (52). Similar to the Q-IVF, the DIVF has been used extensively in research (27,40,54,57,58).

As in any study assessing cumulative live birth rates of IVF treatment, uncertainty remains around end outcomes in those who discontinued treatment, had they continued. This uncertainty will be addressed by the estimation of conservative estimates and, in a sensitivity analysis, optimal estimates for the primary objective MC-CLBR outcome, based on different assumptions of live birth rates in women who discontinued treatment (see Analysis 2 in Table 8). Similarly, the impact on the conservative and optimal MC-CLBR estimates of extending the minimum follow-up to 2 years will also be explored (see Analysis 3 in Table 8).

Further, prescribing patterns of the study drugs are likely to vary to some extent across the study period. If one drug was favored over the other in the early part of the study period, the probability of observing all live births in up to five stimulation cycles using that drug would be higher than for the other one (due to availability of data with longer follow-up). Based on the feasibility assessment of the use of the study drugs in Denmark and Sweden, it is known that the use of rhFSH-alfa biosimilar products has increased gradually, with a relatively larger proportion observed during the latter part of the study period, compared with rhFSH-alfa reference product (37). Hence, it cannot be ruled out that this may lead to a downward bias for the cumulative live birth rate outcomes following COS with rhFSH-alfa biosimilar products.

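### The protocol gives two different cut-offs for the cycles entering time-to-live birth; under the Set 8 wording, with cycle rank as time, unresolved 2020 cycles can count as failed attempts and favour the reference product over biosimilars

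*Protocol*

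**What the plan says.** **Time scale and estimator (Protocol 9.7.3.5).** "The stimulation cycle rank number will be employed as the unit of time". The estimator follows from this: "survival analysis will be performed with the Kaplan-Meier method to estimate the time to the first live birth, expressed as the rank number". The cohorts are then compared with a weighted Cox model. Follow-up stops at the first live birth, the sixth cycle, drug switch, cancer, "death, emigration (Denmark only) or end of study, whichever occurs first". No rule says which rank is given to a woman whose cycle is still open on that last date.

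**End of study (9.1.1 and 9.2.3).** "The study period ends on 31 December 2020 (or last available data) for both study drug comparisons and countries".

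**Which cycles enter.** The wordings differ:
- Section 9.1.1 names the primary outcomes and secondary objective 4 (TTLB), gives a one-year minimum follow-up as the reason, and restricts these analyses to cycles initiated by 31 December 2019. It refers to Sets 1 and 5, but Set 5 in Table 5 is the OHSS set.
- Section 9.7.1 (text) gives one year after stimulation cycle initiation for TTLB.
- Table 5, Set 8, the set assigned to TTLB, reads: "Women who initiated their first-ever stimulation cycle with drug of interest on or before 31 December 2019".
- Table 8, analysis 3, extends the minimum follow-up to two years, again by the date of the first-ever cycle (31 December 2018).

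**Uptake over time (9.9.2).** "the use of rhFSH-alfa biosimilar products has increased gradually, with a relatively larger proportion observed during the latter part of the study period". The section accepts a possible downward bias for biosimilars in cumulative live birth rate outcomes. It does not name TTLB and offers no correction. Table 1 lists calendar year as a baseline characteristic, not as a candidate for the propensity score or for further adjustment.

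**The concern.** Under the Set 8 wording, a woman whose first cycle was in 2019 can start her second to fifth cycles during 2020. A cycle started after about 1 April 2020 cannot show a delivery by 31 December 2020, nine months later.

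On a calendar scale, censoring at end of study would remove the unobserved time. On a rank scale it need not. A woman censored during cycle k is tied with the births at rank k, and Kaplan-Meier and Cox keep tied censored subjects in the risk set. Her open cycle then carries the weight of a completed attempt without a birth. For example, a woman whose first cycle failed in 2019, who conceived in a second cycle in October 2020 and who delivers in July 2021 is recorded as rank 2, no event.

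The loss is larger for a drug whose users started later. The protocol says this of biosimilars, so the distortion would run in the direction of the study hypothesis.

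**Working it through.** The protocol states no TTLB figure, so there is nothing to reproduce. There are three steps.

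**1. Tie convention.** Take four women at rank 2, with one birth and three censored at rank 2. Kaplan-Meier software returns 4 at risk and survival 1 - 1/4 = 0.75. The three open cycles count in full.

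**2. First approximation.** If a share u of the cycles at rank k is unresolved and the true live birth probability is h, the observed probability is about h(1 - u). With h = 0.25 and u = 10.0%, this is 0.225; with u = 18.5%, it is 0.204.

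**3. Simulation with no true drug difference** (400,000 women per cohort).

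- *From the protocol:* biosimilar comparison starting March 2014 (Denmark), first cycles to 31 December 2019, data to 31 December 2020, ranks 1-5.
- *Assumed, not in the documents:* live birth 25% per cycle; 75% return after failure; delivery about 0.75 years after cycle start; 35% of births from frozen transfer, a further 0.2-0.9 years later; mean gap between cycles 0.35, 0.6 or 1.0 year; flat uptake (reference) against linearly rising uptake (biosimilar).
- *True cumulative probability by rank 5:* 1 - 0.75^5 = 0.763.

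| Gap (years) | Uptake | Started under 9 months before end, ranks 1-5 (%) | Observed probability, ranks 1-5 (Set 8 wording) | Cumulative, Set 8 | Cumulative, 9.1.1 rule |
|---|---|---|---|---|---|
| 0.35 | flat | 0, 2.1, 7.6, 11.8, 14.0 | 0.245, 0.237, 0.225, 0.210, 0.206 | 0.720 | 0.755 |
| 0.35 | rising | 0, 4.2, 14.4, 22.0, 25.5 | 0.242, 0.226, 0.198, 0.183, 0.171 | 0.682 | 0.747 |
| 0.6 | flat | 0, 5.8, 12.4, 15.0, 17.3 | 0.246, 0.227, 0.212, 0.205, 0.198 | 0.707 | 0.756 |
| 0.6 | rising | 0, 11.0, 22.7, 27.5, 30.8 | 0.242, 0.207, 0.178, 0.166, 0.155 | 0.652 | 0.742 |
| 1.0 | flat | 0, 10.0, 15.6, 19.8, 26.8 | 0.244, 0.217, 0.199, 0.189, 0.165 | 0.679 | 0.749 |
| 1.0 | rising | 0, 18.5, 28.1, 34.3, 42.1 | 0.242, 0.189, 0.164, 0.146, 0.123 | 0.616 | 0.740 |

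At rank 2 with a 1.0-year gap, the simulated 0.217 and 0.189 lie a little below the approximations 0.225 and 0.204, because late frozen-transfer births are lost as well. The same loss explains the small shortfall at rank 1.

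Spurious rate ratio, flat over rising (Mantel-Haenszel type over ranks, standing in for the Cox ratio), at gaps 0.35 / 0.6 / 1.0:
- Set 8 wording, all ranks: 1.052 / 1.075 / 1.077
- Set 8 wording, ranks 2-5: 1.095 / 1.147 / 1.181
- Every cycle started by 31 December 2019, all ranks: 1.015 / 1.022 / 1.015
- Every cycle started by 31 December 2019, ranks 2-5: 1.021 / 1.031 / 1.025
- Only cycles with at least 1.7 years to resolve, all ranks: 0.997 / 1.004 / 0.997

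A second set of assumptions (live birth 32/28/25/22/20% at ranks 1-5, 70% return, mean gap 6-12 months, 30% of births from frozen transfer) has a true cumulative value of 1 - 0.68 x 0.72 x 0.75 x 0.78 x 0.80 = 77%. The Set 8 wording gives 70-73% (flat) and 65-69% (rising), and an all-rank ratio of 1.05-1.06. Mean rank, restricted to five ranks, rises from a true 2.82 to 2.92-2.96 (flat) and 3.01-3.07 (rising).

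**The case against.** **The protocol already contains the rule that is needed.** Section 9.1.1 restricts the TTLB analysis by cycle date, and the text of 9.7.1 can be read the same way. This stands, and it limits the point: a reader of Table 5 alone might infer that the plan deliberately admits second to fifth cycles up to the end of 2020, but the documents do not settle that. What remains is a contradiction. The set actually assigned to TTLB, and analysis 3, say something else, and 9.1.1 points to the wrong set.

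**The rank at censoring is not stated.** This also stands. Coding a woman with an open cycle at k-1 would remove the fault, and a SAP could do so. But the protocol fixes the time scale, the censoring list and the analysis set, and a literal reading with standard software gives the fault.

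**The bias is partly disclosed.** Section 9.9.2 admits a downward bias for biosimilars, and analysis 3 varies the minimum follow-up. The disclosure does not name TTLB, and analysis 3 again limits only the first-ever cycle, so neither cures the problem.

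**The large figures are not the reported effect.** This is correct. At rank 5 the observed probability can fall to about half the true value (0.123 against 0.25), and a reader might take that as the bias in the result. The planned measure is one ratio over all ranks. Before truncation, rank 1 supplies 1/(1 + 0.5625 + 0.316 + 0.178 + 0.100) = 46% of cycles under the first set of assumptions (0.5625 = 0.75 x 0.75), and it is almost unaffected.

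**Conclusion.** The concern holds as an inconsistency with a material consequence for a secondary objective. If Set 8 is followed and open cycles are coded at rank k, rank-specific and cumulative live birth probabilities are too low and mean or median rank to live birth too high, more so for biosimilars. The spurious all-rank ratio is about 1.05-1.08. For scale, Section 7 cites an adjusted hazard ratio of 1.10 from a study against an hMG product as supporting evidence, and Section 9.5 calls a 5% difference clinically meaningful (said there of MC-CLBR). Under the 9.1.1 rule the ratio is about 1.02.

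These sizes rest on assumed live birth, return and gap rates and on rising against flat uptake; the protocol gives no yearly uptake figures.

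Three wider readings are not supported:
- **HP-hMG.** The protocol places only biosimilar use later, so no differential bias is shown for HP-hMG.
- **Both countries alike.** If Q-IVF data stop on 31 December 2019, Sweden is close to the harmless case. Table 2 expects 10,000 of about 13,000 biosimilar women there.
- **Optimal MC-CLBR.** It would share the fault only if estimated with a rank-based risk set, which Table 8 does not specify.

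**What to change.** 1. State in 9.7.3.5 and in Set 8, for TTLB, that a woman is at risk at rank k only if her k-th stimulation cycle started on or before 31 December 2019, and is otherwise censored at rank k-1.
2. Align 9.1.1, the text of 9.7.1, Table 5 and Table 8 to this rule. Correct the set reference in 9.1.1: Table 5 assigns TTLB and MC-CLBR to Set 8 and CLBR to Set 2.
3. In analysis 3, apply the 31 December 2018 cut-off to each cycle, not only the first-ever one. Two years exceeds the longest delay assumed above (0.75 + 0.9 = 1.65 years), so this analysis would also check the frozen-transfer residual.
4. If the optimal MC-CLBR is estimated with a rank-based risk set, use the same rule there.

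The cost is a few sentences and one filter in the programs. Cycles of rank 2-5 started in 2020 are lost, with a small loss of precision. A small residual from late frozen transfers remains in the main analysis (cumulative 0.740-0.756 against 0.763 in the simulation).
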